The proposed study is a single-arm clinical trial to generate pilot data regarding the safety, feasibility and efficacy of an exercise intervention. Participants will complete a baseline assessment (Visits 1A +/- 1B) at 0 weeks followed by up to 12 weeks of HIIT intervention followed by a repeat assessment (Visits 2A +/- 2B). An overview of the study protocol is provided in Figure 1.

Figure 1: Protocol Overview

Visits 1A/1B and 2A/2B: Visits 1A and 2A will be performed in the inpatient unit of the Clinical and Translational Research Center at the University of Colorado. Each visit will include administration of SF-36 questionnaire, spirometry, and a cardiopulmonary exercise test. Peripheral IV will be placed for the purpose of venous blood draws for complete blood count, ferritin and untargeted metabolomics analysis.(1) Radial arterial line will be placed for continuous blood pressure monitoring and measurement of arterial blood gas and lactate. Participants will be oriented to VO2max testing protocol. Baseline fitness will be assessed by questioning to determine step protocol. Once arterial line is in place, participants will complete a symptom-limited CPET on an upright stationary bicycle. Workload will begin at 0 Watts and increase every minute by 10-30 W (based upon pre-testing questioning) to achieve volitional exhaustion with maximum workload at 8-12 minutes.(22) Heart rate and rhythm, blood pressure, oxygen saturation, and gas exchange parameters (VO2, VCO2, and minute ventilation) will be continuously measured. Borg RPE, arterial blood gas and lactic acid will be measured at rest, every 4 minutes during exercise, and at peak exertion. Attainment of a high-quality VO2max will be determined based upon achieving one or more of the following: a plateau in VO2; attainment of predicted VO2max, work rate, or heart rate; respiratory exchange ratio >1.15, and Borg Scale rating 9-10 on a 0-10 scale.(6) Peripheral venous blood draw for untargeted metabolomics analysis will be repeated at peak exercise.

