Anticipated risks of HIIT training include fatigue, shortness of breath and leg discomfort, and participants will be counseled of these risks. Additionally, study team will closely monitor for adverse events through observation as well as participant report. Adverse events will include the following: minor – hypotension (BP < 90/60), lightheadedness, hypoxemia (SpO₂ <80% for >60 seconds),(24) chest pain, arrhythmia, or need to terminate exercise for another reason; major – major adverse cardiac event (stroke, myocardial infarction or cardiovascular death) or hospitalization. Exercise session will be terminated for any minor adverse event and PI and study safety monitor will be notified. Patient will be referred to Emergency Room if any member of the study team or the participant feel referral is indicated. Additionally, participant will be evaluated by PI prior to engaging in any future sessions. If further participation is felt to be of risk to the patient by either PI or the study’s safety monitor, then participation in study will be terminated. Major adverse events are not anticipated, but if any should occur patient will be transported immediately to the Emergency Room. HIIT has been studied in various populations including those with good health but sedentary lifestyle,(8) moderate to severe asthma,(17) and coronary artery disease,(25) and similar or identical HIIT regimens to that described in this protocol studies have demonstrated >80% compliance without attributable adverse events.(8, 25) Additionally, the study design includes an initial baseline assessment with symptom-limited CPET. If the initial CPET identifies safety concerns with completing the study exercise protocol, those concerns will be addressed prior to participant completing any further intervention. If unable to be addressed then the participant will be removed from the study. Therefore, the proposed protocol is anticipated to be safe for participants.

Home exercise: In addition to HIIT sessions described above, participants will perform three sessions / week of 40 minutes aerobic exercise at moderate intensity (Borg rate of perceived exertion 12-14). Home exercise will be prescribed to minimize the risk of confounding from

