paradoxical decrease in non-HIIT day physical activity (an effect described in the literature of exercise training interventions).(26) The home exercise program will include a three-week “phase-in” period as described in the protocol above. Participants will keep a diary of home exercise as described above in “Study Design and Research Methods” that includes a field for symptoms and adverse events. Study personnel will collect the diary at 4-week intervals and at that time will also question participant regarding any adverse events not reported through other means. Home exercise has been studied in populations including those with chronic lung disease and pulmonary arterial hypertension without significant attributable adverse effects.(27, 28) Additionally, as described above all participants will undergo baseline CPET and if risks to engaging in an exercise regimen are identified they will be addressed prior to any further intervention.

Risks to a pregnant woman, embryo or fetus: Due to physiologic changes of pregnancy which are anticipated to impact response to exercise training, pregnant women will be excluded from this study. Women of child-bearing age will complete a urine pregnancy test prior to testing during Visit 1. If the test is positive, the participant will be informed and removed from the study. Additionally, participants will be counseled to avoid pregnancy during the study and will be removed from the study should pregnancy occur.

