Hypothesis 2C: *Staff will spend approximately 2 hours/participant in exercise supervision and coordination. Staff will report that level of supervision and time commitment was appropriate and feasible.* Staff time spent in exercise supervision will be calculated by [hours spent supervising exercise / number of individuals supervised simultaneously + hours spent scheduling and/or coordinating]. Staff's qualitative assessment of feasibility will be collected via narrative report.

Specific Aim 3:

Hypothesis 3A: *HIIT induces positive right ventricular and pulmonary vascular remodeling, improving right ventricular performance and exertional cardiac output, reflected by decreased glycolytic metabolites on peripheral venous metabolomics; improved exertional pulmonary artery systolic pressure on TTE; and improved oxygen pulse, ventilatory efficiency, and dead space fraction on CPET. Additionally, markers of left ventricular diastolic function on TTE will improve reflecting general positive training adaptations of HIIT.*(8) Metabolomics heat maps, partial least squares discriminant analysis, and t-test or ANOVA will be performed to compare pre- vs post-exercise training glycolytic metabolites. Pulmonary artery systolic pressure on TTE and oxygen pulse, ventilatory efficiency, and dead space fraction on CPET will be analyzed using descriptive statistics and compared pre- and post-exercise program by t-test. Resting left ventricular diastolic function (E/e') will be analyzed using descriptive statistics and compared pre- and post-exercise training by t-test.

Hypothesis 3B: *HIIT improves VO2max among patients with deployment-related respiratory disease.* VO2max will be analyzed using descriptive statistics and compared pre- and post-exercise training by t-test.

Hypothesis 3C: *HIIT improves dyspnea and health-related quality of life (SF-36).* SF-36 pre- and post-exercise training will be analyzed using descriptive statistics and compared pre- and post-exercise training by t-test.

Results will be analyzed according to an intention-to-treat protocol. A p-value of <0.05 will be used to establish statistical significance. Statistical analysis will be performed using SAS v 9.4 (SAS Institute Inc., Cary, NC, USA). For metabolomics data, the MetaboAnalyst 4.0 package will be used for analysis and XY graphs will be created using GraphPad Prism 8 (GraphPad Software Inc., La Jolla, CA, United States).

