Sample Size: Based on published data in patients with asthma,(17) who represent the most similar disease phenotype undergoing HIIT interventions reported in the current literature, a sample size of 10 is anticipated to provide 90% power to detect a difference in VO₂max of 2 ml/kg/min after HIIT, assuming a standard deviation of 1.8 ml/kg/min at an alpha = 0.05 and up to a 10% dropout rate. For the purpose of this pilot study, a sample size of 12 is anticipated to yield sufficient preliminary data regarding cardiac and pulmonary vascular abnormalities and safety, feasibility and efficacy of HIIT in the described patient population with the intent of future analysis in a larger study.

F. Summarize Knowledge to be Gained:

This study will generate hypotheses of pulmonary vascular and cardiovascular contributions to exercise intolerance after airborne hazards exposure, particularly among patients who currently remain undiagnosed with traditional evaluation. Additionally, it will demonstrate safety and feasibility of HIIT in this population and generate preliminary data regarding its efficacy in improving cardiopulmonary performance and symptoms of exercise intolerance. **The results will 1) inform larger investigations of extrapulmonary mechanisms of post-deployment dyspnea, particularly pulmonary vascular and cardiovascular abnormalities and 2) provide justification for a randomized controlled trial of different exercise modalities' efficacy in improving exertional dyspnea after airborne hazards exposure.**

G. Funding:

This study will be supported by the Department of Veterans Affairs Airborne Hazards and Burn Pits Center of Excellence (AHPCE) Pilot Project Program Award #FY2023-001 and a CTRC Microgrant. The contents do not represent the views of the AHPCE, U.S. Department of Veterans Affairs or the United States Government.

H. References:

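### The pre-post tests of VO2max and SF-36 are labelled intention-to-treat but can use only people measured at Visit 2A, and the protocol ends participation, with no further outcome collection described, for some who stop

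*Combined protocol and SAP*

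**What the plan says.** The statistical text is in section III, Data Analysis Plan. After the Aim 3 hypotheses it states: "Results will be analyzed according to an intention-to-treat protocol". It does not say who belongs to that set.

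For Hypothesis 3B the plan is: "VO2max will be analyzed using descriptive statistics and compared pre- and post-exercise training by t-test". For Hypothesis 3C it is: "SF-36 pre- and post-exercise training will be analyzed using descriptive statistics and compared pre- and post-exercise training by t-test". Study Design and Research Methods schedules one baseline assessment, "followed by up to 12 weeks of HIIT intervention followed by a repeat assessment (Visits 2A +/- 2B". VO2max and SF-36 are taken only at Visits 1A and 2A. No interim outcome visit, early-termination assessment, imputation rule or missing-data sensitivity analysis is described. The one mixed model, under Hypothesis 1C, relates pulmonary artery systolic pressure to VO2max and plays no part in the pre-post comparison.

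Section III.D sets out who leaves:

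- HIIT intervention: if an investigator or the safety monitor judges further participation a risk, "then participation in study will be terminated".
- Same paragraph, on safety concerns found at the baseline exercise test: "If unable to be addressed then the participant will be removed from the study".
- Risks to a pregnant woman, embryo or fetus: participants "will be removed from the study should pregnancy occur".

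Potential Scientific Problems (feasibility of the training program) points the other way. Injured people switch to continuous training or pause, and people who miss targets are helped with barriers. Neither group is removed. The Sample Size paragraph allows for "up to a 10% dropout rate".

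**The concern.** An intention-to-treat label leads a reader to expect that everyone who entered is represented in the result. A pre-post change does not exist for someone without a Visit 2A value, and the plan gives no other way to represent that person. The gap is wider than an unstated missing-data policy, because the protocol's own rules produce some of the missing values: they end study participation rather than training alone. Removal for safety may be related to how a person was responding, so the loss may not be random.

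The estimates are meant to inform larger investigations and to help justify a randomized trial (Summarize Knowledge to be Gained). A reader taking the gain as intention-to-treat would not know that removed people are absent from it. With 12 enrolled, one person is enough to move the mean.

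**Working it through.** **1. Who can enter the test.** Change = Visit 2A value − Visit 1A value. Without Visit 2A there is no change. I read the t-test as paired, which the plan does not state. An unpaired version could keep a removed person's baseline but would still hold no outcome for that person.

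**2. How the plan's own sample size treats dropouts.** Inputs from the Sample Size paragraph: difference 2 ml/kg/min, SD 1.8, alpha 0.05, power 90%, dropout up to 10%. I read 1.8 as the SD of the change and alpha as two-sided; neither is stated. By the normal approximation:

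n = ((1.960 + 1.282) × 1.8 / 2)² = 8.51, rounded up to 9; then 9 / 0.90 = 10.

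This reproduces the stated 10. On this reading the sizing treats dropouts as lost from the analysis, which fits an observed-pairs test and not an analysis of everyone enrolled. Other readings give other numbers (an exact two-sided paired t-test needs 11, or 13 after dropout), so this is supporting evidence only.

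**3. Possible size for VO2max.** Assume 12 enrolled, an observed mean gain of 2.0, d people without Visit 2A, and a true change c in each of them. The mean over all enrolled is (2.0 × (12 − d) + c × d) / 12. With c = 0, the overstatement is 12 / (12 − d) − 1.

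| d | Share of 12 | Pairs used | Mean if c = 0 | Overstatement if c = 0 | Mean if c = −1 |
|---|---|---|---|---|---|
| 1 | 8.3% | 11 | 1.83 | 9% | 1.75 |
| 2 | 16.7% | 10 | 1.67 | 20% | 1.50 |
| 3 | 25.0% | 9 | 1.50 | 33% | 1.25 |

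The planned dropout is up to 10% × 12 = 1.2 people, so d = 1 is the planned case. The rows for 2 and 3 are stress cases. The values of c are assumptions.

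**4. Scale against sampling error.** With 11 pairs the standard error is 1.8 / √11 = 0.54. The planned-case gap is 2.0 − 1.83 = 0.17, and 0.17 / 0.54 = 0.31, about a third of a standard error. Exact two-sided paired-t power with 11 pairs is 91.2%. Keeping the twelfth person in at zero change gives about 89.0%.

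The documents give no expected SF-36 change or SD, so no corresponding size can be worked out for that outcome.

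**The case against.** The strongest reply is that the plan never defines intention-to-treat. In a single-arm study the term can reasonably mean analysing people whatever their adherence. The feasibility text supports this, since injured and non-adherent people stay in, can reach Visit 2A and can be analysed. That part of the label can be met. A reader might infer from the t-test that only people who finish training are analysed; the documents do not support that. Even so, the reply does not cover people whose study participation is ended, and for them the plan offers neither an outcome nor a rule.

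A reader might also infer that anyone with a safety problem is removed. The text is narrower. A minor adverse event ends the session and leads to evaluation. Removal follows only if an investigator or the safety monitor judges continuing a risk, or if a concern from the baseline test cannot be addressed.

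A third tempting inference is that the gain is certainly biased upward. The documents do not show it. Withdrawal is allowed for any reason, pregnancy need not relate to response, and the protocol cites similar regimens with over 80% compliance and no attributable adverse events. Overstatement is plausible, but its direction and size are unknown.

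Finally, the planned case is small against sampling error, and the protocol already concedes that the lack of a control group limits efficacy conclusions. Both points stand. They limit the consequence and leave the mismatch between label and method in place.

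**Conclusion.** The point holds in limited form. As written, the efficacy result is an observed-case analysis of people with both visits, carrying an intention-to-treat label that the stated test cannot deliver for those removed. That only people with both visits are analysed is inferred from the method and the silence on missing data; nothing in the documents offers another route. In the planned case, with one of 12 missing and zero change assumed, 2.0 ml/kg/min observed corresponds to 1.83 over all enrolled. Larger gaps need more dropout than planned, or worse outcomes in the missing person. For a single-arm pilot this should be corrected, but it does not undermine the study.

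**What to change.** - Reconcile the termination wording in section III.D with the intention-to-treat statement by separating stopping exercise from ending outcome collection.
- Seek the SF-36 from everyone with a Visit 1A who still consents. The protocol already allows paper or the MyCap application. Any decision on repeat exercise testing stays with the investigator and safety monitor.
- Pre-specify a sensitivity analysis for VO2max and SF-36 that assigns zero change to anyone without a post value.
- Report the number without Visit 2A, with reasons.
- Call the t-test result observed-case rather than intention-to-treat.

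A mixed model is not a remedy here. With one arm and two time points, people with only a baseline value shift the mean change only through baseline differences. The model also assumes data missing at random, so it would not correct outcome-related loss.

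The cost is a few sentences, at most a few extra questionnaires and one extra analysis. The sensitivity estimate will look slightly less favourable if anyone is missing and the observed mean change is a gain.
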